### 5. Informed Consent

a. Procedure for obtaining Informed Consent from all participants (or their parent[s] or guardian[s])? Describe who will obtain consent. (Attach Informed Consent form.)

The study will be explained on an internet page that people can access if they are interested

in participating (Appendix B). Potential subjects will read the Informed Consent document and will be allowed to contact any of the researchers if they have questions. People who choose to participate will be directed to a SurveyMonkey site that will require they agree to the Informed Consent to be able to continue to the questionnaires. Subjects will be able to withdraw from the research at any time; if they request that their data be deleted, they will lose access to the Pilates videos as access to those videos are linked to their subject identifier and data.

The Informed Consent form will ask subjects to attest to the fact that they are between 18-70 years old and that, to the best of their knowledge, they are physically able to perform the exercises safely.

We request a waiver of obtaining written informed consent on the basis that all interaction with subjects is on-line and it is not practical to obtain signed informed consent. The on-line informed consent form advises that by proceeding with the survey, they are consenting to participate.

b. If minors or other participants unable to provide legal informed consent are involved, outline procedures to be used in obtaining their agreement (assent) to participate, in addition to the consent of the parent(s) or guardian(s). (Attach assent form or statement.)

No minors will participate in this study. The questionnaires will ask each subject to verify that he/she is 18 or older. Realistically, we will not be able to verify their age. However, risk involved in participation is very low, and is no greater than daily life where they could choose to do Pilates or share some personal information on-line.

## 6. Study Design and Methods

a. Procedure for data collection and intervention, including duration of subject involvement: The intervention is provided through an on-line Pilates module commercially available at https://[name]/strengthen-your-hypermobile-core/. "Strengthen Your Hypermobile Core" has 5 modules. Subjects will be asked to complete the modules in order, as the modules build upon one another. However, subjects may repeat any modules at any time, with the goal of completing all 5 modules within the 8 week period. This allows subjects the flexibility to customize their participation by using the modules they feel are most helpful. Users who typically access this Pilates course have this same flexibility so, while it adds variability to the intervention, it better reflects how the program is actually used.

Subjects will be asked to do their Pilates practice while watching the videos (not from memory) to ensure that they are performing techniques optimally. Each module lasts 25 minutes, but includes some resting activities so modules are not vigorous or fatiguing for most people. Nonetheless, subjects will be instructed to omit activities that they feel they cannot do safely. Subjects can pause a session to add more rest breaks, if needed, or stop and complete a session later. Subjects will commit to doing 3 Pilates modules per week, for a total of 75-90 minutes/week (depending on the exact length of the modules they do). The commercial application of this on-line Pilates course provides the ability to track access to each module, so we will have data regarding compliance and which modules are used at which time. Data about module utilization will be linked to the subject's self-created research code, which will keep this data anonymous as we cannot link the self-created research code to any identifiable individual.

Subjects will complete questionnaires before starting the on-line Pilates modules. Completing these questionnaires on SurveyMonkey is likely to take 30-45 minutes. These questionnaires are described in detail in section b, below.

Subjects will receive a weekly email, encouraging them to continue doing Pilates at least 3 times/week. This email will also ask them to complete some narrative questions on SurveyMonkey regarding whether they have had any problems completing the Pilates

sessions and, if so, why. We will also ask if they have any comments about the modules or about their experience. We will also ask about any changes in pain, either related to the Pilates practice, or unrelated. The contact email will also remind them that they can contact one of the PI (JD) if they have questions or problems with the Pilates, or (LR) if they have any questions about research participation.

At the end of 8 weeks, subjects will be asked to repeat the initial questionnaires on SurveyMonkey, and comment on their experience doing the Pilates. This is likely to take about 60 minutes. Subjects will continue to have access to the Pilates modules and we will encourage them to continue using the modules. We will track whether individuals do access the modules over the next 6 months.

Six months after subjects complete the 8 week exercise session, we will contact each subject again and ask him/her to repeat the initial questionnaires on SurveyMonkey, and again comment on whether they felt the Pilates was helpful.

We will also include an 8-week wait-list group constructed from subjects asking to participate after we have already recruited 225 subjects. This wait list is primarily because we do not want to be so overwhelmed by participants that we cannot manage them effectively (responding to questions about the Pilates, sending out follow-up surveys, etc.). Also, a wait-list group would provide a control group (albeit not randomly selected). All participants who do not start in the initial group will be asked if they still want to participate in a wait-list group; if they do, we will contact them 8 weeks after their initial surveys were completed, ask them to repeat the surveys, then start them in the Pilates program.

### **b. Measurement tools.** (Attach questionnaires and surveys as labeled appendices.)

- Demographic questionnaire (see Appendix C)
- \* The Bristol Impact of Hypermobility questionnaire (BloH) will be used to assess changes in pain, fatigue, self-efficacy and function.(Palmer, 2017. see Appendix D)
- The Revised Body Awareness Rating Questionnaire (R-BARQ). 12 questions. (Dragesund, 2018, Appendix E).
- The Tampa Scale of Kinesiophobia (TSK, 11 item version) will be used to assess kinesiophobia. (Woby, 2005. See Appendix F)
- The International Physical Activity Questionnaires (IPAQ) Short Form is a validated survey assessing physical activity during work, sport, and leisure time; this will be used to monitor activity level.(Booth, 2000. See Appendix G)
- Weekly Email questions for qualitative information and adverse event reporting. (Appendix H)
- Post-intervention questions for 8 weeks and 6 months (Appendix I)

### c. Equipment interfacing with subjects:

Subjects will interface with the questionnaires and Pilates modules through their own computers or other electronic devices. Subjects will be asked to use a yoga mat or padded floor, small ball or towel roll, and elastic exercise band or inelastic strap to provide feedback during some of the exercises.

**d. If deception is necessary, justify and describe debriefing procedures.** (Attach debriefing statement as labeled appendix.) No deception is involved.

### e. Analysis of outcomes:

- Quantitative data will be coded and entered into Excel, reviewed for outliers, and transferred to SPSS
- Descriptive statistics related to demographics and initial scores for BIoH, IPAQ, TSK-11, R-BARQ
- Descriptive statistics related to subjects use of the different modules (which Pilates modules were used during each of the 8 weeks and overall), and continued use of the modules through the 6 month follow-up.

- Repeated Measures ANOVA comparing pretest, post-test (8 wk) and 6 month after post-test: BIOH, IPAQ, TSK-11, R-BARQ
- ANOVA comparing change over 8 weeks for the Pilates group vs. the wait-list group: BloH, IPAQ, TSK-11, R-BARQ
- Regression analysis using IPAQ, TSK-11, R-BARQ to predict quality of life and function as measured using BloH before intervention, after intervention (including compliance) and 6 months later (including compliance).
- Qualitative analysis of the narrative (email) information using content analysis using the following process:(Bengtsson, 2016)
  - o Decontextualization to identify meaning units, create code list
  - o Recontextualization to verify that all important information has been coded
  - o Categorization to organize themes, with triangulation by investigators
  - Compilation to formulate conclusions, audit, member check if subjects agree

We understand that the lack of a randomized control group makes our current design less rigorous than a randomized control trial (RCT), but having a wait-list comparison group makes the design stronger.

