The current study will repeat the questionnaires at the end of the 8 week intervention, to assess change, and again 6 months later to determine whether any changes have been maintained. We will also monitor whether subjects continue to do the Pilates exercises at 6 months, either using the videos or on their own. If findings in the current study are encouraging, a more formal randomized control trial would be an appropriate progression. The qualitative data may provide useful information about how to implement a follow-up study more effectively.

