# 3. Objectives and Hypotheses

- 1. Implement a pilot study to assess whether this on-line Pilates course for people with hEDS/HSD results in beneficial changes when compared to a wait-list comparison group. We understand that the evidence will not be strong with a non-random comparison group, but having a comparison group is better than not having one. We hypothesize that 8 weeks of this specialized Pilates training will result in:
  - a. Decreased pain and symptoms, improved function and quality of life (measured using the BloH),
  - b. Increased physical activity (measured using IPAQ with additional questions)
  - c. Improved body awareness (R-BARQ) and less dysfunctional breathing patterns (R-BARQ)
  - d. Decreased fear of movement (TSK-11).
- 2. Pilot test the proposed outcome measurement tools for such a future study. We are looking for basement and ceiling effects, as well as change over time.
- 3. Explore whether certain patterns of implementation of the on-line course are associated with better outcomes. For example, is it better to repeat one module multiple times before moving on, or to move around among modules? This will be descriptive correlational data.
- 4. Gather qualitative data to better understand factors that may influence compliance or maximal benefit. These data can inform future research into either Pilates or use of internet-accessible exercise training for this population. This qualitative information also provides insights into factors that influence participation in exercise within this population, and whether certain patterns are observed among people who benefit from the program compared to those who do not.

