## d. Incentives and compensation

Subjects will be able to use the on-line Pilates course "Strengthen Your Hypermobile Core" during the study (8 weeks of intervention and 6 months of follow-up) for free . Subjects who complete the study (8 week and 6 month questionnaires) will be given permanent access to this course as incentive to complete the study.

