# f. Methods for providing anonymity or confidentiality. For research involving patients, describe how HIPAA requirements will be met.

Each subject will create his/her own identifying code based on personal information. The identifier will be created using the following criteria:

- The 3 first letters of the month (in English) of your MOTHER'S birthday (e.g., SEP)
- YOUR 2-digit birthday date (e.g., Ø8 for May, 8th) (01-31)
- The first letter of YOUR MIDDLE NAME; enter X if you do not know or have a middle name (e.g. M for Mary) (A-Z)
- The total number of OLDER SIBLINGS you have, including living, deceased, and half (e.g., 0 if you are an only child; enter 9 if you have 10 or more siblings) (0-9)

For the examples given above, the identifier would be SEP08M0 (SEPØ8MØ). Identifiers using these variables have been shown to be highly repeatable, and there are processes for linking identifiers that are mismatched by one element. (Yurek, 2008) Once data collection is complete, all subject email addresses will be deleted from the research data. The email address will be retained by [name] as long as these individuals choose to use the on-line Pilates program, in the same way that typical customer information is retained. Research subjects may request that their emails be deleted by [name] if they no longer want to access the Pilates modules.

g. Plan for destroying private, identifiable data at the end of the research project. (You must request approval for continuation annually until all private, identifiable data has been destroyed.) Subjects' email address is the only identifying information that is collected during this research. Once a subject has completed the study, that person's email address will be deleted from the research data. Identifying codes will be discarded after all data for a given individual have been collected and entered into the computer of the primary researcher, [name].

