## **Appendix H**

### Weekly email/SurveyMonkey

Thank you for participating in "Assessing the Impact of Internet-Guided Pilates Training on People with Hypermobility."

We hope you are continuing to do the Pilates exercises, but remember that you should only do what you feel is appropriate for you. As long as you continue to respond to the questionnaires, you are still an active research subject, independent of whether or how much Pilates exercise you do.

You may contact [name] if you have questions about the Pilates program, but please do not share information regarding your response to the research questions in SurveyMonkey, as [name] is "blinded" to the research data (for scientific validity and to protect your private information, she is not supposed to know how individual subjects respond to the research questions). Please do not Reply to this email. If you would like to contact [name] with questions about the Pilates program, please email her directly at: [contact].

Please click on the following link to go to SurveyMonkey, where we will ask you some questions about your participation. These questions will take 10-30 minutes, depending on how much you would like to share about your experience.

SL	RVEY M	MONKEY CONTENT FOR WEEKLY FOLLOW-UP EMAILS (not included in the emails)  The 3 first letters of the month (in English) of your MOTHER'S birthday (e.g., SEP)  YOUR 2-digit birthday date (e.g., Ø8 for May, 8th)  The first letter of YOUR MIDDLE NAME; enter X if you do not know or have a middle name (e.g. M for Mary)				
	•	The total number of OLDER SIBLINGS you have, including living, deceased, and half (e.g., 0 if you are an only child; enter 9 if you have 10 or more siblings)  In this example, your identification code would be SEP08M0 (SEPØ8MØ)				
ра	ticipatio	ng questions are part of the research data collection, and will not be analyzed until your n is complete. Feel free to email [name] ( [contact] ) if you have about the Pilates activities, and would like a response.				
PΙε	ase ans	wer questions 1 and 2 every week.				
1. 2.	you think is due to the Pilates exercises? Yes / No a. If so, briefly describe. [narrative response]					
rea	son, pl	e increased pain or other symptoms, either due to the Pilates exercises or any other ease modify or omit any or all Pilates exercises that do not feel safe to do and contact h care provider as appropriate.				

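### Section 6e has no rule for missing surveys; a classical three-visit repeated-measures ANOVA would drop everyone without a 6-month survey from the within-group 8-week and maintenance contrasts

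*Combined protocol and SAP*

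**What the plan says.** Section 6e (Analysis of outcomes) lists two quantitative comparisons for the BIoH, IPAQ, TSK-11 and R-BARQ:

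- Within group, over three surveys: "Repeated Measures ANOVA comparing pretest, post-test (8 wk) and 6 month after post-test".
- Between groups, over two surveys: "ANOVA comparing change over 8 weeks for the Pilates group vs. the wait-list group".

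The only data-handling step is: "Quantitative data will be coded and entered into Excel, reviewed for outliers, and transferred to SPSS". The supplied text contains no analysis population, imputation rule, complete-case statement or named SPSS procedure.

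The two comparisons serve different purposes. Objective 1 in Section 3 asks whether the course "results in beneficial changes when compared to a wait-list comparison group", which the between-group ANOVA addresses. Section 2 collects the last survey "again 6 months later to determine whether any changes have been maintained", and that reading can come only from the three-visit analysis.

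The plan does work against loss. Under Section 4d, people who complete both follow-ups "will be given permanent access to this course as incentive to complete the study". Appendix H tells subjects: "As long as you continue to respond to the questionnaires, you are still an active research subject". On the self-generated codes, Section 7f states: "Identifiers using these variables have been shown to be highly repeatable", and it allows linkage of codes that differ in one element. These measures concern retention and record linkage. None says how a survey that never arrives is handled in the analysis.

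**The concern.** A classical repeated-measures ANOVA (GLM Repeated Measures in SPSS) needs a complete set of visits for each person. Someone with a pretest and an 8-week score but no 6-month score is removed entirely, so a loss at the third visit reaches back into the first contrast. The same happens to someone who misses week 8 but returns the 6-month survey.

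Three things follow if that form is used:

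- The within-group 8-week change is estimated on fewer people than supplied the data.
- If the people lost differ in their observed scores, the 8-week and maintenance contrasts are biased, in a direction that cannot be known in advance.
- The report could carry two 8-week changes for the same group, one from people with both early surveys and one from 6-month completers, with nothing to explain the gap.

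Loss is foreseeable. Section 5a allows withdrawal at any time, and the last survey comes six months after the course ends. The completion reward is continued access to the course, which may be worth more to people it helped. That would tie return to 8-week change, but it is an inference and the documents do not say so.

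**Working it through.** The plan gives no power, SD, correlation or attrition figure, so there is nothing of its own to reproduce. What follows shows the possible size under stated assumptions.

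**Inputs.** From the documents: 225 in the immediate-start group (Section 6a); an equal number next in the wait-list (Section 4e), so 450 if both groups' Pilates periods are analysed. Assumed: 80% return the 8-week survey (225 × 0.8 = 180; 450 × 0.8 = 360); outcome SD 1 at each visit; correlation 0.7 between any two visits; no true change; 20%, 30% or 40% of those 180 or 360 lost by 6 months. Negative values mean apparent improvement.

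**1. Does the method need all visits?** A classical repeated-measures routine was run on 225 simulated people, 60 of them without the third visit. It refused to fit because the data were unbalanced. Those 60 must be removed before it will run.

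**2. Precision of the 8-week contrast.** The SD of change is √(2(1 − 0.7)) = 0.775. The half-width is 1.96 × 0.775/√n.

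| Loss by 6 months | n kept | Half-width | Ratio to n = 180 |
|---|---|---|---|
| none | 180 | 0.113 | 1 |
| 20% | 144 | 0.127 | √(180/144) = 1.12 |
| 30% | 126 | 0.135 | √(180/126) = 1.20 |
| 40% | 108 | 0.146 | √(180/108) = 1.29 |

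The ratio does not depend on the correlation. At 30% loss the half-widths are 0.146 and 0.175 for correlation 0.5, and 0.092 and 0.110 for correlation 0.8. With both groups they are 0.080 (n = 360) and 0.096 (n = 252).

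**3. Bias among completers.** Simulated with 2,000,000 people per scenario:

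| Loss depends on | Contrast | 20% | 30% | 40% |
|---|---|---|---|---|
| nothing observed | 8-week | 0.00 | 0.00 | 0.00 |
| 8-week change, log-odds 0.5 per SD | 8-week | -0.07 | -0.11 | -0.15 |
| 8-week change, log-odds 0.5 per SD | maintenance | +0.04 | +0.06 | +0.07 |
| 8-week level, log-odds 0.5 per SD | 8-week | -0.03 | -0.04 | -0.06 |

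Hand checks agree:

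- Loss following change: the 8-week bias is roughly −(loss rate) × slope × SD of change. At 30%, −0.3 × 0.5 × 0.775 = −0.116.
- Loss following level: multiply the shift in level by (1 − 0.7). At 30%, −0.3 × 0.5 × 0.3 = −0.045.
- Maintenance: later change regresses on 8-week change with slope (0.7 − 1)/(2 × 0.3) = −0.5, so its bias is half the 8-week bias with opposite sign. −0.11 gives about +0.055.

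Reversing the slope on change, so that better responders are lost, reverses every sign.

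**4. Rejection rate of the three-visit F test** (nominal 5%, no true change, completers only). From 180 starters the rate is 5% if loss is unrelated to scores. With slope 0.5 on change it is 17%, 28% and 41% at 20%, 30% and 40% loss. With slope 0.25 on change it is 7%, 11% and 14%. With slope 0.5 on level it is 9% at 30% loss. From 360 starters with slope 0.5 on change it is 29%, 51% and 71%.

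**5. After the fix.** A likelihood model with unstructured covariance on all surveys gave bias 0.00 for all contrasts and 5–6% rejection when loss followed observed change. Its precision gain for maintenance is small. At 30% loss unrelated to scores, the residual variance of the 6-month score given the first two is 1 − 2(0.49)/1.7 = 0.4235, leaving 0.6 − 0.4235 = 0.1765 explained. The half-width is 1.96 × √(0.4235/126 + 0.1765/180) = 0.129, against 0.135 for completers.

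**6. A second set of assumptions.** With correlation 0.6, a true 8-week change of −0.30 SD that is fully maintained, and 30% loss, slopes of 0.5 to 1.0 give completer estimates of −0.43 to −0.52 at 8 weeks and +0.06 to +0.11 for maintenance. Likelihood-type estimates returned −0.30 and 0.00.

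**The case against.** The case for leaving the plan alone has several parts.

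- **The defect is conditional.** The plan does not name GLM. What is documented is silence; listwise deletion is the natural consequence but still an inference. This stands, and the point is worded accordingly. The silence matters all the same, because two analysts following Section 6e could analyse different people.
- **The 8-week change is available elsewhere.** The between-group ANOVA needs two surveys only, and the Pilates group's mean change is an ordinary output of it. This stands for the immediate-start group. It does not cover the three-visit test or the maintenance reading. Section 6e also states no analysis population for the between-group test, so its fuller numbers are what the method permits rather than what the plan promises.
- **The maintenance bias is small.** +0.04 to +0.07 SD sits inside a half-width of 0.135. Its sign means that losing poorer responders makes maintenance look worse, not better. Both statements are right under these assumptions.
- **The large rejection rates rest on one slope.** Nothing in the documents supports 0.5; at 0.25 the rates are 7% to 14%. The test also pools three visits, so these rates do not measure false claims of maintenance. This stands, and they should be read as a range running from no inflation upward.
- **A mixed model does not cure everything.** Loss at 6 months driven by the unseen 6-month score remains. This stands and is the main limit of the fix.
- **This is a pilot with a retention incentive.** That limits the weight of the point. It does not argue against a change that needs no new data.

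**Conclusion.** The concern holds as a conditional, limited point. Section 6e leaves missing surveys unaddressed. In its classical form the three-visit ANOVA discards collected 8-week data from anyone without a 6-month survey, and makes the within-group and maintenance readings depend on who returns that survey.

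If loss is unrelated to scores, the cost is precision only: the 8-week interval is 12% to 29% wider at 20% to 40% loss. If loss follows observed 8-week change at log-odds 0.5 per SD, the bias is 0.07 to 0.15 SD for the 8-week contrast and 0.04 to 0.07 SD, with opposite sign, for maintenance. A gentler slope gives less and a reversed slope flips the signs. The actual size and direction are unknown, because the attrition rate, the correlation and the cause of loss are all assumed here.

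The between-group test for Objective 1 is not touched. The change should be made because it is cheap; the trial's main comparison does not depend on it. Confidence is medium.

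**What to change.** In Section 6e:

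1. Replace the repeated-measures ANOVA with a linear mixed model (SPSS MIXED, REML, visit as a categorical factor, unstructured covariance) using every available survey.
2. Report the number analysed at each visit.
3. Compare baseline and 8-week scores of people with and without the 6-month survey.
4. If the wait-list group's later Pilates period is included, state that its end-of-wait survey is the pre-Pilates visit.
5. State that the model corrects only for loss explained by observed scores. It does not correct week-8 loss driven by the unseen 8-week score, or 6-month loss driven by the unseen 6-month score; the maintenance result should be worded with that limit.
6. Leave the between-group ANOVA of 8-week change as planned.

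The cost is a change of wording and some extra analysis in software the plan already uses. There is no new data collection and no added burden on subjects. The gain lies mainly in the 8-week contrast and in removing bias linked to observed scores; for maintenance the precision gain is slight (half-width 0.135 to about 0.13 at 30% loss).
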